#### Sample Size

Assuming uniform 3-year accrual and 2-year follow-up, a two-sided logrank test with a sample size of 132 (66 patients per treatment arm) will achieve 80% power at  $\alpha=0.05$  to detect a difference between 50% and 70% progression free survival at 2 years. This difference corresponds to median survival times of 24 months and 46.6 months, respectively, and a hazard ratio HR=1.94, assuming exponential survival distribution (The HR is based on a 2-year PFS that would be clinically meaningful – 50% to 70%, the preclinical animal data, and the hazard ratio associated with activated mTOR in patient samples. As no historical data exists for this type of trial these assumptions are rational given what information is available). Assuming 20% loss to follow-up, **N=160 patients (80 per arm) will be enrolled.**

The stratified logrank test will also be used for the analysis of secondary endpoints, specifically comparing PFS in patients with evidence of Akt/mTOR pathway activation (mTOR+ vs. mTOR-) in the adjacent normal mucosa. Whereas progression-free survival is expected to be similar among mTOR+ and mTOR- patients in the everolimus arm, mTOR+ patients on placebo are expected to do worse than mTOR- patients. Assuming 50% mTOR+ prevalence in each arm (n=33/arm), a two-sided logrank test will have 80% power and  $\alpha=0.05$  to detect a difference in 2-year PFS of 70% vs. 40.7%, which corresponds to median time to progression or death of 46.6 and 18.5 months, and a hazard ratio HR=2.5. Similarly, assuming 40% prevalence of upregulated Akt/mTOR pathway (n=26/arm), a two-sided logrank test will achieve 80% power at  $\alpha=0.05$  to detect a difference between 70% vs. 36.4%

2-year PFS, which corresponds to median time to progression or death of 46.6 and 16.5 months, and HR=2.8. While the detectable differences are quite large, they are comparable to those observed in other studies – for example, patients with FOE+ and FOE- in the retrospective study (Nathan et al, 1999) had median PFS of 82 and 31.5, which corresponds to HR=2.6.

## 7

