## 3 Investigational plan

### 3.1 Overall study design

This is a randomized, double-blind, phase 2 study of everolimus versus placebo. Randomization will be stratified for disease stage and type of local therapy (IVa surgical vs. IVa non-surgical vs. IVb) as well as treating institution. Eight to 16 weeks after completion of definitive, curative-intent therapy for locally advanced SCCHN, potentially eligible subjects will be consented and randomized to receive either everolimus or placebo for a maximum of 1 year. Subjects will be evaluated prior to starting therapy; 4, 16, 32 and 52 weeks after starting therapy; and then at least every 4 months for a minimum of 2 years (those enrolled early will be followed for 3 years).

Radiographic assessments (CT, PET-CT, PET and/or MRI) will be conducted prior to initiating therapy and every 4-6 months for 2 years then every 6 months in year 3. Not all patients will be followed for 3 years at end of study. Minimum radiographic follow-up will be 2 years for all patients. For those subjects enrolled early, longer follow-up will determine secondary endpoints such as PFS and OS.

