### 3.2 Study population

#### 3.2.1 Patient population

160 subjects (80 per arm, everolimus vs. placebo)

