### 3.4.2 Visit schedule

**Table 3-4 Evaluation and visit schedule**

Examination	Screening/ Baseline	Week									
		4	16	32	52	64	80	96	112	128	144
Informed consent	X										
No Evidence of Disease	X										
Inclusion/exclusion criteria	X										
Tissue Biopsy	X										
Radiographic assessment	X										
Physical examination	X										
ECG	X										
Laboratory test	X	X	X	X	X	X	X	X	X	X	X
Research Blood Draw	X	X	X		X						
HBV-DNA, HbsAg, HBs Ab, HBs Ab, HCV-RNA-PCR^6	X										
Patient Questionnaire	X										
Follow Up Form^8		X	X	X	X	X	X	X	X	X	X

See Section 3.2.2

See Section 3.4.7; Tissue biopsy must have been obtained PRIOR to curative intent therapy

Baseline radiographic assessment (CT, PET-CT, PET and/or MRI as appropriate) must be preformed within 12 weeks of starting everolimus. CT, PET-CT, PET and/or MRI as appropriate should be performed at least every 4-6 months in years 1 and 2 then every 6 months in year 3.

Baseline assessments must be performed within 7 days of starting everolimus. Hemoglobin, platelets, total white blood cell count (WBC), and differential; sodium, potassium, chloride, bicarbonate, calcium, glucose, creatinine, blood urea nitrogen, albumin, total protein, SGOT (AST), SGPT (ALT), total bilirubin, alkaline phosphatase, uric acid, phosphorus, serum lipid profile (triglycerides, total cholesterol, HDL and LDL); PT (INR) evaluation only at baseline unless otherwise indicated. Patients should be fasting at the time of the blood sampling.

Blood draw for serum, whole blood and optional PBMC isolation (see Section 3.4.7). Serum will be drawn at screening, weeks 4, 16 and 52. Whole blood will be drawn at weeks 4, 16 and 52. Optional PBMC will be drawn at screening and week 4.

All patients should be **screened** for hepatitis risk factors and any past illnesses of hepatitis B and hepatitis C infection. If the patient has any of the risk factors outlined in section 3.4.1 then serologic testing must be done.

All patients should fill out the Patient Questionnaire prior to first dose. See the Study Procedures manual.

See the Study Procedures Manual

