New adverse events for patients who discontinue the study will not be recorded past their date of discontinuation but events that are ongoing will be followed, if feasible, until they resolve. All patients will be followed for survival.

A weekly report of delinquent or pending documents will be forwarded to [name] (U of C Events Only). All delinquent reporting (greater than 10 days from event occurrence) must include documentation of reason for delinquency and may require implementation of an action plan.

SAEs that have not resolved at the time of reporting should have a follow up written report within 10 calendar days of resolution. This includes any pregnancies in which the outcome, including spontaneous or voluntary termination, details of birth, and the presence or absence of any birth defects, congenital abnormalities or maternal and newborn complications should be reported.

Once the appropriate SAE documents have been received, the University of Chicago Cancer Center Clinical Trials office forwards these to the Principal Investigator. The Principal Investigator should comment on the outcomes of the event or problem including likely relationship to study drug. The Principal Investigator should also indicate whether he/she concurs with the details of the report provided by the study investigator and provide any recommendations for actions to be taken in response to the SAE.

Once the University of Chicago Cancer Center Clinical Trials Office receives the Principal Investigator's report, they will forward all documents to the IRB, research nurse, all participating institutional PI's, the FDA, and Novartis [contact]).

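### The 80% power for 132 patients needs PFS follow-up to a common cut-off that the assessment schedule does not provide, and 160 enrolled covers 17.5% loss, not the stated 20%

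*Combined protocol and SAP*

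**What the plan says.** The Sample Size section (under 6.1) states: "Assuming uniform 3-year accrual and 2-year follow-up, a two-sided logrank test with a sample size of 132 (66 patients per treatment arm". It claims 80% power at two-sided α = 0.05 for 50% versus 70% PFS at 2 years, under exponential survival with medians of 24 and 46.6 months and a hazard ratio of 1.94. It continues "Assuming 20% loss to follow-up" and arrives at 160 enrolled. Section 3.2.1 repeats the total: "160 subjects (80 per arm, everolimus vs. placebo".

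On follow-up, Section 3.1 sets a minimum of 2 years for everyone and adds that "those enrolled early will be followed for 3 years" and that "Not all patients will be followed for 3 years at end of study". The imaging footnote to Table 3-4 says scans "should be performed at least every 4-6 months in years 1 and 2 then every 6 months in year 3", and the visit columns of that table end at week 144. Section 3.3.2 puts unblinding at the conclusion of the study, about 2 years after accrual ends. Section 4.6 adds: "All patients will be followed for survival".

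**The concern.** With 3 years of accrual and a cut-off 2 years after the last entry, the first patient has 60 months of potential follow-up and the last has 24. A power figure built on that pattern counts progressions and deaths in years 4 and 5 for early entrants. The schedule contains no progression assessment in those years. Separately, 20% of 160 is 32, which leaves 128 and not the 132 on which the 80% rests.

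This is the only power statement for the primary comparison. If the result is negative, readers will use it to judge how large an effect the trial could have missed, so it should describe the follow-up and losses that the plan sets out.

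**Working it through.** **Inputs, all from the Sample Size section.** Two-sided α = 0.05, 1:1 allocation, 66 per arm, 2-year PFS 50% and 70%, exponential survival, uniform 36-month accrual, 24 months of further follow-up, 20% loss, 160 enrolled. The 36-month limit is taken from Section 3.1 and Table 3-4. The loss timings are assumptions, because the documents give none.

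**Hazards.** λ_P = ln 2/24 = 0.02888 and λ_E = −ln(0.7)/24 = 0.01486 per month. HR = 1.943; medians 24.0 and 46.6 months. These agree with the plan.

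**Events needed for 80% power.**
- Freedman: (1.960 + 0.842)² × [(HR+1)/(HR−1)]² = 76.4
- Schoenfeld: 4 × (1.960 + 0.842)² / (ln HR)² = 71.1

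**Power from d events.** Freedman: Φ(√d·(HR−1)/(HR+1) − 1.960). Schoenfeld: Φ(√d·ln HR/2 − 1.960).

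**Reproducing the plan's figure (common cut-off, 24 to 60 months).** The event probability is 1 − (e^(−24λ) − e^(−60λ))/(36λ):
- placebo: 1 − (0.500 − 0.177)/1.040 = 0.689
- everolimus: 1 − (0.700 − 0.410)/0.535 = 0.458

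Events = 66 × (0.689 + 0.458) = 75.7. Power is 79.6% (Freedman) or 82.4% (Schoenfeld), so the stated 80% reproduces. It does not if everyone is followed for exactly 24 months: 66 × (0.5 + 0.3) = 52.8 events, 64.4% / 67.5%. The sponsor's calculation therefore used the common cut-off.

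**Follow-up limited to 36 months.** Entrants in the first 24 accrual months have exactly 36 months; the last third have 24 to 36. The event probability is 1 − [(e^(−24λ) − e^(−36λ))/(36λ) + (24/36)·e^(−36λ)]:
- placebo: 1 − [0.141 + 0.236] = 0.623
- everolimus: 1 − [0.214 + 0.390] = 0.396

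Events for 132 = 66 × (0.623 + 0.396) = 67.3, which is 8.4 fewer.

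**Loss allowance.** 132/0.80 = 165. 160 × 0.80 = 128. 1 − 132/160 = 17.5%. For comparison 132 × 1.20 = 158.4, so 160 is what results from multiplying by 1.20 instead of dividing by 0.80.

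**Losses censored over time.** With a constant loss rate η = −ln(0.8)/T, the event probability at follow-up t is λ/(λ+η) × (1 − e^(−(λ+η)t)), averaged over entry. For 160 with the 36-month limit:
- 20% by month 24: 80 × (0.548 + 0.344) = 71.3 events
- 20% by month 36: 80 × (0.572 + 0.360) = 74.5 events
- 20% by month 12: 80 × (0.485 + 0.301) = 62.9 events

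The rate is taken to continue after month T. The month-12 case therefore implies 1 − 0.8² = 36% lost by month 24 among patients without an event, so it is a harsh reading of a 20% allowance.

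| Setting | Events | Power, Freedman / Schoenfeld |
|---|---|---|
| 132, common cut-off | 75.7 | 79.6 / 82.4% |
| 128, common cut-off | 73.4 | 78.4 / 81.2% |
| 132, 36-month limit | 67.3 | 74.8 / 77.8% |
| 128, 36-month limit | 65.2 | 73.5 / 76.5% |
| 160, limit, 20% lost by month 36 | 74.5 | 79.0 / 81.8% |
| 160, limit, 20% lost by month 24 | 71.3 | 77.2 / 80.1% |
| 160, limit, 20% lost by month 12 | 62.9 | 72.0 / 75.0% |
| 160, common cut-off, 20% lost by month 24 | 78.2 | 80.9 / 83.6% |
| 160, common cut-off, 20% lost by month 36 | 82.3 | 82.8 / 85.4% |

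**The case against.** The power figure follows correctly from its stated assumption, and Section 3.3.2 places the end of the study where that assumption needs it. Section 3.1 speaks of minimum follow-up and never calls 3 years a maximum. PFS events include deaths, as the section's wording for the biomarker subgroups shows ("which corresponds to median time to progression or death of 46.6 and 18.5 months"), and survival follow-up could capture late deaths. All of this stands, so the 36-month limit is an inference from the schedule. What remains is that early entrants are given a stated 3 years, no visit or scan is scheduled after it, and survival follow-up does not schedule assessments for progression.

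It is also fair to say that the practical effect is small. Simulated unstratified logrank power for the 160 with the limit is 79.3% (20% lost by month 24) or 81.0% (by month 36), closer to Schoenfeld than to Freedman.

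Three stronger readings are tempting, and the documents do not support them.
- *The enrolled trial is underpowered.* The 160 stay near 80% under two of the three loss timings examined. They fall clearly below it only with early loss, or if lost patients contribute nothing and the limit also applies.
- *The limited-follow-up figures are lower bounds, because late deaths can only add events.* That holds for late events alone. Earlier loss lowers the figures. So does ending assessment at week 144, about 33 months (132 patients: 64.7 events, 73.2 / 76.2%). Section 6.1 specifies a stratified test, with institution among the randomization strata in Section 3.1. With assumed numbers of strata, simulated power for the 160 with 20% lost by month 24 falls from about 80% unstratified to about 79% with 3 strata and 76% with 15.
- *The 36-event interim in Section 4.7 is wrong.* It implies 36/0.50 = 72 events, which is compatible with the Schoenfeld requirement (71.1), with 128 at the common cut-off (73.4) and with 160 under the limit with loss by month 24 (71.3). It is not an error.

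**Conclusion.** The point holds in two parts. The loss figure is plain arithmetic and certain: 160 covers 17.5% loss, and at 20% the 128 remaining patients cost about 1 point of power at the common cut-off. The follow-up mismatch is conditional. The 80% for 132 needs 24 to 60 months of PFS follow-up; if follow-up stops at 36 months, power is about 75-78% for 132 evaluable patients and 74-77% for 128.

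For the 160 enrolled the consequence is modest and depends on when losses occur: about 77-82% or about 72-75% in the cases above. All figures assume exponential survival at the design hazards, uniform accrual and an unstratified test. The stated 80% is therefore plausible, but the plan does not show it for the schedule and loss allowance it describes.

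**What to change.** In the Sample Size section, either replace 20% with 17.5%, or keep 20% and state the power for 128 patients.

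Then reconcile follow-up in one of two ways:
- State in Sections 3.1 and 3.4.2 that PFS is followed to the common cut-off 2 years after last entry, and add assessments after year 3 for early entrants. The existing calculation then applies.
- Keep the 3-year maximum and restate events and power for it in the Sample Size section, naming how lost patients are counted and when losses are assumed to occur. No power range should be printed without that assumption.

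The second route costs only wording and, depending on the loss assumption, a somewhat lower stated power. The first adds visits and scans for patients still event-free at month 36 who entered in the first 24 accrual months. Event-free probabilities at month 36 are 0.354 and 0.586, mean 0.470; 0.470 × 24/36 = 0.313, or about 50 of 160 before losses, for up to 24 months each. Neither route adds patients.

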### Secondary

- Toxicity of everolimus versus placebo as adjuvant therapy
- Site of disease progression (locoregional vs. distant) in subjects treated with everolimus versus placebo
- Incidence of second primary tumors in subjects treated with everolimus versus placebo
- Prevalence of Akt/mTOR pathway activation in locally advanced SCCHN
- Determine correlation between progression free survival (PFS) and the degree of activation of the Akt/mTOR pathway biomarkers in tumors and adjacent mucosa treated with everolimus versus placebo
- Determine if PTEN status is predictive marker of Everolimus sensitivity

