### **3.4.7 Research tests**

Tissue obtained (PRIOR to curative intent therapy) from the diagnostic biopsy/panendoscopy and/or during surgical resection, PBMC, serum and whole blood samples will be used for the correlative studies. The studies will be performed in [name] research laboratory (LSUHSC, Shreveport, LA) and at the University of Chicago.

The tumor suppressor gene PTEN is an important regulator of the Akt/mTOR pathway and often found to be mutated in HNSCC patients. Hence we will evaluate PTEN status by FISH and mutation analysis in all patients. Correlation between PTEN status and the sensitivity to Everolimus will be determined.

We will determine the correlation of the Akt/mTOR pathway activation [pAkt(S473), pmTOR(S2448), pS6(S235/236), p4EBP1(T37/46) and eIF4E] by IHC and/or western blot (when available) analysis in tumors and adjacent normal mucosa. The Kaplan-Meier method with logrank test and/or Cox Regression model will be used to compare PFS between HNSCC patients with different degree of biomarker upregulation in tumors but more importantly in the normal surrounding mucosa as previous studies have shown that patients with mTOR activation in the margins are at a higher risk for recurrence.

Upregulation of the Akt/mTOR pathway is associated with an increased survival of cancer cells and their decreased sensitivity to chemo- and radiotherapy. Also it was shown for some types of cancer that tumors with heightened Akt activation are more sensitive to mTOR inhibition. Based on these evidences we hypothesize that the risk of disease recurrence correlates with the degree of activation of the Akt/mTOR pathway biomarkers and that the patients with heightened Akt activation will benefit the most from adjuvant therapy with everolimus. Thus we will test the hypothesis that either the adjacent normal mucosa or tumor tissue or both from SCCHN patients who recurred after treatment will have higher pAkt/pmTOR expression as compared to the tissue samples from the SCCHN patients who did not recur after treatment.

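### The plan asks whether PTEN and Akt/mTOR status predict everolimus benefit but has no treatment-by-marker test, and its 80% marker power figures answer a different question and leave the 70% comparator unnamed

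*Combined protocol and SAP*

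**What the plan says.** Three places state or imply that everolimus should work differently according to marker status.

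- Section 2 (Secondary) lists the aim "Determine if PTEN status is predictive marker of Everolimus sensitivity".
- Section 3.4.7 hypothesises that "the patients with heightened Akt activation will benefit the most from adjuvant therapy with everolimus".
- Section 6.1 (Sample Size) expects similar PFS by mTOR status on everolimus, whereas "mTOR+ patients on placebo are expected to do worse than mTOR- patients".

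The analyses attached to these are:

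- Section 3.4.7, PTEN: "Correlation between PTEN status and the sensitivity to Everolimus will be determined". No model or test is named.
- Section 3.4.7, Akt/mTOR: Kaplan-Meier with logrank and/or Cox regression of PFS by degree of marker upregulation, and marker expression in recurred versus non-recurred patients.
- Section 6.1 (Sample Size): a stratified logrank test "specifically comparing PFS in patients with evidence of Akt/mTOR pathway activation (mTOR+ vs. mTOR-) in the adjacent normal mucosa".
- Section 6.1 (Statistical methods): regression for the treatment effect, adjusted for prognostic factors.

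Two power statements follow in Sample Size. The first reads "Assuming 50% mTOR+ prevalence in each arm (n=33/arm), a two-sided logrank test will have 80% power", for 70% versus 40.7% two-year PFS (HR 2.5). The second reads "assuming 40% prevalence of upregulated Akt/mTOR pathway (n=26/arm), a two-sided logrank test will achieve 80% power", for 70% versus 36.4% (HR 2.8). The benchmark offered for these differences is a marker contrast: "for example, patients with FOE+ and FOE- in the retrospective study".

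**The concern.** Whether a marker is predictive depends on whether the everolimus-versus-placebo hazard ratio differs between marker groups. Comparing PFS between marker groups shows whether the marker is prognostic. Adjusting the treatment effect for other factors does not address the question either. Even a marker difference seen on placebo and not on everolimus does not by itself show that the marker predicts benefit, because the two within-arm results are never compared with each other. Under the plan as written, a marker that worsens PFS equally in both arms could be reported as predicting everolimus benefit.

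The 80% figures add to the problem. They sit directly after a sentence describing a predictive pattern, so a reader may take them as power for that pattern. The text also does not say who the 70% group is.

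**Working it through.** **Inputs.** From Section 6.1 (Sample Size): exponential PFS, 36 months of uniform accrual plus 24 months of follow-up, two-sided 0.05, 66 evaluable per arm (80 enrolled), marker prevalence 50% or 40%, and two-year rates 70%, 40.7% and 36.4%. From Section 3.1: early patients are followed for 3 years, used below as an alternative cap of 36 months.

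**Step 1: reproduce the 80%.** Hazard λ = -ln(S)/24. Event probability P(λ) = 1 - [exp(-24λ) - exp(-60λ)]/(36λ).

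| 2-year PFS | λ per month | P, no cap | P, 36-month cap |
|---|---|---|---|
| 70% | 0.01486 | 0.458 | 0.396 |
| 40.7% | 0.03746 | 0.7765 | 0.718 |
| 36.4% | 0.04211 | 0.813 | 0.758 |

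The hazard ratios are 0.03746/0.01486 = 2.52 and 0.04211/0.01486 = 2.83, and the medians are 46.6, 18.5 and 16.5 months, all as printed.

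Lachin-Foulkes power is Φ(z), with z = {√N·|λ1-λ2| - 1.96·√[v(λ̄)(1/q1+1/q2)]} / √[v(λ1)/q1 + v(λ2)/q2]. Here v(λ) = λ²/P(λ), q1 and q2 are the group fractions, and λ̄ = q1λ1 + q2λ2.

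| Contrast | Power |
|---|---|
| 66 vs 66, 70% vs 50% (primary) | 80.3% |
| 33 vs 33, 70% vs 40.7% | 79.9% |
| 26 vs 26, 70% vs 36.4% | 80.0% |
| 40 vs 26, 70% vs 36.4% | 88.0% |
| 40 vs 26, 70% vs 40.8% | 80.1% |

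Other approximations and a logrank simulation put the two marker cases at 78.5-84.9% and the 40 vs 26 case at 89-91%, so the pattern does not depend on the formula.

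**Step 2: which groups fit?** The preceding sentence makes mTOR+ on placebo the natural owner of the low rate. The 70% group could be mTOR- on placebo or mTOR+ on everolimus.

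- At 50% prevalence, 66 × 0.5 = 33 in each group on either reading.
- At 40% prevalence, 66 × 0.4 ≈ 26 mTOR+ per arm. Everolimus versus placebo within mTOR+ is 26 vs 26, which gives the stated 80%. mTOR+ versus mTOR- within one arm is 26 vs 40, which gives about 88%; on that reading, 80% is already reached at about 70% vs 40.8%.
- Pooling both arms (66 vs 66 at 50% prevalence) would give about 97-99%, so that was not meant.

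The 40% case therefore fits a treatment contrast, or else ignores the unequal split, while the announced comparison and the FOE benchmark both point to a marker contrast.

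**Step 3: power for the predictive question.** The test is on the log ratio of hazard ratios, with SE = √(Σ 1/d) over the four arm-by-marker cells, where d is the expected number of events in a cell. Power = Φ(|ln ratio|/SE - 1.96), and the ratio detectable with 80% power = exp(2.80·SE).

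Assumptions: both everolimus groups at 70%; placebo mTOR+ at 40.7% (50% prevalence) or 36.4% (40% prevalence); marker known in everyone. Placebo mTOR- is either about 59%, which keeps the placebo arm at the design's 50% (case A), or 70% (case B).

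Example (66 per arm, 50% prevalence, case B, no cap): events are 33 × 0.458 = 15.1 in three cells and 33 × 0.7765 = 25.6 in the fourth. SE = √(3/15.1 + 1/25.6) = 0.487, and the ratio is 2.52. Power = Φ(0.924/0.487 - 1.96) = 47.5%, and the detectable ratio is 3.92.

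| Per arm | Follow-up | A, 50% / 40% prevalence | B, 50% / 40% prevalence | Detectable ratio |
|---|---|---|---|---|
| 66 | no cap | 21% / 28% | 47.5% / 57% | 3.75-3.95 |
| 66 | 36-month cap | 19% / 25% | 43% / 51% | 4.1-4.3 |
| 80 | no cap | 24% / 32.5% | 55% / 65% | 3.3-3.5 |
| 80 | 36-month cap | 22% / 29% | 50% / 59% | 3.6-3.8 |

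Cox simulations agree within about 0.02.

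**Cross-check on the protocol's event count.** Section 4.7 equates 36 events with 50% of those expected, which implies 72. Spread evenly over four cells, SE = √(4/18) = 0.471 and the detectable ratio is exp(2.80 × 0.471) ≈ 3.75.

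**The case against.** The strongest reply is one of proportion. These are secondary correlative aims in a 160-patient phase 2 trial. Sample Size already concedes that the detectable differences are large, and only PTEN is called a predictive marker in the objectives: the listed Akt/mTOR objective is a correlation with PFS, for which a prognostic analysis is planned. An interaction test with the power shown above would rarely settle the matter.

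Much of this is fair. It supports an exploratory label and modest claims, and it makes the gap clearest for PTEN. It does not remove the gap for Akt/mTOR, because Section 3.4.7 states a differential-benefit hypothesis and Sample Size states the matching pattern. The word exploratory in Section 6.1 attaches to the covariate-adjusted regressions, not to the marker aims. Low power is a reason to report an estimate with its interval; it does not make a marker comparison answer the predictive question.

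Several stronger readings are tempting and not supported:

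- A reader might infer that the 80% is miscalculated. It is not; it reproduces.
- A reader might infer that neither rate can be assigned to a group. The low rate can reasonably be read as mTOR+ on placebo; only the 70% comparator is open.
- A reader might infer that no tissue is specified. Sample Size names adjacent normal mucosa, and Section 3.4.7 gives it priority and asks for mucosa slides. What is missing is the protein and the cut-off that define mTOR+.
- A reader might infer that the unnamed comparator hides a shortfall. If a within-placebo marker contrast was meant, the printed 80% understates the power of that contrast.

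**Conclusion.** The point holds. The documents pose predictive questions for PTEN and Akt/mTOR, and no planned analysis tests whether the treatment effect differs by marker. The 80% figures are correct for a two-group logrank test and do not apply to the predictive question, for which power is about 19-57% at 66 per arm and 22-65% at 80 per arm, with a detectable ratio of hazard ratios of about 3.3-4.3. Those ranges rest on the protocol's detectable rates taken as true, an assumed placebo mTOR- rate between about 59% and 70%, and complete marker data. They say nothing about PTEN, whose prevalence is not given.

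The unnamed 70% comparator is a lesser matter of clarity that only the sponsor can settle. A reader might go on to doubt the primary result; nothing here bears on it.

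**What to change.** 1. For PTEN (one stated definition) and for one pre-named Akt/mTOR marker and cut-off in adjacent normal mucosa, fit a Cox model for PFS with treatment, marker and treatment-by-marker terms, stratified by the combined stage and local-therapy factor. Report the ratio of hazard ratios with a 95% CI, and rest any predictive statement on that term alone.
2. In Sample Size, name the 70% comparator and the arm or arms behind each 80% figure. If a marker contrast within placebo was meant, restate the 40%-prevalence case as 26 versus 40.
3. State that the predictive analyses are exploratory and that interaction power is well below 80%, with the range and assumptions above, and that the range does not cover PTEN.

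The cost is a little more analysis work, including agreeing the cut-off in advance, and a less favourable power statement for secondary aims. No new patients or samples are needed.
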